6.2. Derived Variables

Table 8 defines the derived variables for study parameters.

Table 8: Derived Variables and Definition

Variable	Definition
Height (cm)	If height is recorded in inches, then height is equal to the recorded value multiplied by 2.54 and then rounded to 1 decimal place.
Weight (kg)	If weight is recorded in pounds, then weight is equal to the recorded value multiplied by 0.454 and then rounded to 1 decimal place.
Body Mass Index(BMI)	BMI will be computed using height measured at screening and body weight measured at respective visits as, $BMI(kg/m^2) = Weight(kg) / Height(m)^2$ and then rounded to 1 decimal place.
Relative Day	The day of the first dose of the study drug will be considered as relative Day 1.
Study Day	Study day will be computed as: Date of Assessment – Date of relative day 1
Baseline	Baseline is defined as the last assessment made prior to the first dose of study drug administration.
Change from Baseline	Change from baseline will be derived as: post-baseline visit/time point value – the baseline value
Last Date in Study	Last date in study is defined as: 
 • The date of the 14-day follow-up if the subject completes the study. • The date of the early termination visit if the subject is terminated early from study at a non-scheduled visit. • The date of the latest scheduled visit if the subject is terminated early from study at a scheduled visit or lost to follow-up.
Duration (Hours) of Study Drug Exposure (Multiple-Dose phase)	Date/Time of Last Dose – Date/Time of First Dose
Duration of Morphine use (hours)	Date/Time of Last Dose Morphine – Date/Time of First Dose Morphine
Duration (Days) of AE	AE end date – AE start date + 1
AE Onset Day	AE start date – Date of first dose + 1

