Table 4) will be collected following randomization. The FLACC will be used for subjects in Groups A and B. The NIPS will be used for subjects in Groups C and D. All subjects will then be closely monitored for pain and their pain score will be recorded at least hourly until their pain score is ≥ 4 on the FLACC or ≥ 3 on the NIPS, at which time they will be administered study drug (oxymorphone HCl immediate release oral liquid for Groups A and B; IV oxymorphone HCl for Groups C and D) or placebo. Subjects in Groups A and B must be able to tolerate oral intake prior to receiving oxymorphone oral liquid. Morphine-NCA (section 8.1.4) will be initiated coincident with but not earlier than study drug/placebo administration, and this time will be designated as day 1 time zero. No food or oral liquid restrictions will be imposed around the time of dosing. All subjects will receive morphine-NCA rescue as needed. Subjects will undergo subsequent pain assessments at half-hour intervals post first dose in the multiple-dose phase (Table 4). Following dose 1, subsequent doses should be administered q4-6h PRN but no less than 4 hours apart, and at least 20 minutes have elapsed since the last bolus NCA rescue. The last dose of study drug will be administered no later than 18h post first dose. (All subjects must receive a minimum of 3 doses of study drug in the multiple-dose phase). PK and additional assessments will occur at fixed intervals throughout the multiple-dose phase, as outlined in section 3. Food consumption will be recorded from the period 1 hour prior to administration of study drug through EOT assessment; record all times that any food was consumed and what food was consumed (DAT, DAT-soft, FF, CF, water, formula, breast milk).

Following first administration of study drug, procedures and assessments will include the following:

- Blood samples for PK analysis should be collected immediately prior to each dose. Post-dose vital signs, respiratory assessments, and neurological assessments will be recorded at 0.5, 1, 2, 3, and 4 hours after administration of first dose of study drug; and at 0.5, 1, and 2 hours after administration of subsequent doses.
- Continuous telemetry.
- Continuous pulse oximetry.
- AEs and concomitant medications will be monitored throughout the multiple-dose phase.
- Pain assessments (using FLACC or NIPS; see Appendix C or Appendix D, respectively) will be recorded every 0.5 hours through EOT.

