3. STUDY DESIGN AND MEASURES

3.1. Study Design

This is a Phase 3, post marketing study conducted to meet a Pediatric Research Equity Act (PREA) commitment. The study comprised an open-label, single-dose, dose selection phase and a randomized, double-blinded, active controlled multiple-dose phase to characterize the efficacy, safety, tolerability, and PK of oxymorphone HCl in pediatric subjects with acute moderate to severe postoperative pain for whom an opioid may be determined to be an appropriate treatment option. It is a multicenter study intended to be conducted at up to 25 sites. At the time the study was prematurely stopped, the study was conducted at 3 clinical sites.

The study was designed to be conducted in 2 phases: single-dose phase and multiple-dose phase. The single-dose phase was an open label dose selection phase intended to determine the dose (for each age group) in the multiple-dose phase (Figure 1) based on the recommendation of an IDMC. The multiple-dose phase included a double-blinded assessment of oxymorphone HCl vs. placebo.

Each study phase consisted of the following planned study periods:

- Screening period (within 5 days of surgery)

- Post-surgery evaluation
- Treatment period occurring after surgery
- End-of-treatment (EOT) assessment 24 hours after the last dose of study drug; and
- 2 follow-up contacts (at 3 ±1 and 14 ±2 days after the last dose of study drug).

All subjects were enrolled preoperatively up to 5 days before surgery with the expectation that they would require intravenous (IV) access after surgery and postoperative analgesia with an opioid.

It was intended to enroll subjects sequentially to each of the below mentioned four age groups with recruitment of older infants and toddlers preceding recruitment of the youngest age subjects:

- Group A: 6 months – <2 years (up to and inclusive of 729 days)
- Group B: 61 days – <6 months (up to and inclusive of 179 days)
- Group C: 31 days – 60 days
- Group D: 0 – 30 days

In the single-dose phase, it was planned that up to 3 cohorts of 5 subjects for each age group would receive oxymorphone HCl and in the multiple-dose phase a single cohort of 10 subjects were planned be enrolled to receive study drug or placebo in 1:1 allocation ratio for each age group. However, by the time Group B was to enroll subjects, the study was suspended (only 5 subjects were enrolled in Group B for cohort 1).

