3.10. Vital Signs

Vital sign measurements included systolic and diastolic blood pressure, respiratory rate, pulse, body temperature, and oxygen saturation. Length (height) and weight were recorded at screening only and body mass index (BMI) will be computed. Refer to Table 8 for BMI derivation.

For the single-dose phase, vital sign measurements were taken at Screening, post-surgery evaluation visit, baseline visit, 0.5, 1.0, 1.5, 2.0, 3.0, 4.0, 6.0, 8.0 and 24-hours post dose.

For the multiple-dose phase, vital sign measurements were taken at Screening, post-surgery evaluation visit, baseline visit, 0.5, 1.0, 2.0, 3.0 and 4.0 hours after administration of first dose of study drug; and at 0.5, 1.0 and 2.0 hours after administration of subsequent doses.

Clinically significant abnormalities (as per Investigator’s criteria) in vital sign values were considered as an AE or SAE as appropriate.

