4.5.1.1. Treatment Emergent Adverse Events

TEAEs are defined as any AEs that occur or worsen (increase in severity) after treatment initiation through the 14-day follow-up period.

Refer to Section 6.3.1.1 to identify TEAE status when start date of an AE is unknown.

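### SAP Table 8 dates AE onset and duration by calendar day in a trial that runs on hours, and the TEAE tables pool events before and after end of treatment.

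*SAP*

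**What the plan says.** SAP 6.2, Table 8, gives AE onset day as "AE start date – Date of first dose + 1" and AE duration, in days, as "AE end date – AE start date + 1". Neither uses clock time. Two other rows of that table do: study-drug exposure in the multiple-dose phase is "Date/Time of Last Dose – Date/Time of First Dose" and morphine use is "Date/Time of Last Dose Morphine – Date/Time of First Dose Morphine", both in hours.

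SAP 4.5.1.1 defines TEAEs as AEs that "occur or worsen (increase in severity) after treatment initiation through the 14-day follow-up period". SAP 7.8.2 restricts the AE summary tables to TEAEs unless stated otherwise. It breaks them down by system organ class and preferred term, severity, relatedness, seriousness and effect on study drug. It has no split by period, and it names no table of onset day or AE duration.

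The trial's own time scale is short. SAP 3.10 places the post-dose single-dose vital signs at "0.5, 1.0, 1.5, 2.0, 3.0, 4.0, 6.0, 8.0 and 24-hours post dose". In the multiple-dose phase up to five doses are possible, and "The last dose of study drug will be administered no later than 18h post first dose" (Protocol 8.1.6). SAP 3.1 sets the "End-of-treatment (EOT) assessment 24 hours after the last dose of study drug".

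After EOT the conditions change. Protocol 10.1.5 allows opioid or non-opioid analgesics per standard of care, and Protocol 12.1.1 and SAP 3.8.1 have post-operative pain recorded as an AE from then on. For medications, SAP 4.4 already draws a line between concomitant and follow-up use at 24 hours after the last dose.

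**The concern.** Surgery, anaesthesia, standard-of-care opioid, study drug and NCA morphine can all fall on one date. Protocol 8.1.4 starts NCA with the first study-drug dose, and AEs are collected from consent, so peri-operative events are in the database.

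The SAP drops efficacy and PK (sections 3.4, 3.15 and 8), which leaves safety as the whole of the abbreviated report. SAP section 1 says that the data monitoring committee's recommendation rested on the risk of respiratory depression in the youngest infants. To judge an apnoea or a desaturation, a reader needs to know how many hours after which drug it began and whether it lasted minutes or most of a day. The two derived variables do not carry that information.

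The pooling is a second, separate matter. One TEAE count mixes events under study drug with events that arise up to two weeks later, possibly on other opioids and under a different rule for recording pain.

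**Working it through.** The plan states no figure on this point, so there is none to reproduce. The check applies the Table 8 formulas to clock times. The documents give no time of peak effect and no dosing hour. Assumptions: peak effect 0.5 to 2 hours after dosing; next morning means 07:00 on the date after dosing; the dosing hour is varied.

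**1. Onset day, dose at 10:00**

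| Event | Hours from dose | Table 8 onset day |
|---|---|---|
| Same time, previous date | −24 | 0 |
| 04:00 | −6 | 1 |
| 09:00 | −1 | 1 |
| 10:30 | +0.5 | 1 |
| 11:00 | +1 | 1 |
| 12:00 | +2 | 1 |
| 18:00 | +8 | 1 |
| 07:00 next date | +21 | 2 |
| 10:00 next date | +24 | 2 |

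Six of these times, spread over 14 hours on both sides of the dose, share Day 1. Earlier dates and the next morning do not.

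**2. How far this depends on the dosing hour**

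Take dosing times uniform over 24 hours and a peak x hours after dosing.
- An event 1 hour before dosing and one at the peak share a date with probability (24 − 1 − x)/24. This is 93.8% for x = 0.5, 91.7% for x = 1 and 87.5% for x = 2. For doses between 08:00 and 20:00 it is 100%.
- An event at the peak and one at 07:00 the next date share a day only if the peak falls after midnight, with probability x/24: 2.1%, 4.2% and 8.3%. For doses between 08:00 and 20:00 it is 0%.

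**3. Several doses**

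Onset is counted from the first dose only. At the minimum 4-hour spacing, doses at 10:00, 14:00, 18:00 and 22:00 all fall on Day 1, so the onset day cannot show which dose came before an event.

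**4. Duration**

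- 10:00 to 10:10 on one date: 0 + 1 = 1 day.
- 01:00 to 23:00 on one date (22 hours): 0 + 1 = 1 day.
- 23:55 to 00:05 (10 minutes): 1 + 1 = 2 days.

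**5. Pooling across EOT**

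- Single-dose phase: EOT is at 24 h and the TEAE window runs to 14 × 24 = 336 h. The part after EOT is 336 − 24 = 312 h, or 13 of 14 days. The whole window is 336/24 = 14 times the period to EOT.
- Multiple-dose phase, last dose at 18 h: EOT is at 18 + 24 = 42 h and the window ends at 18 + 336 = 354 h. The ratio is 354/42 = 8.4.

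These are shares of time, not of events, and they leave out the ±2-day window on the call.

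**6. The pre-dose/post-dose boundary**

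SAP 6.3.1.1 covers completely unknown AE start dates and partial dates whose month and year precede the first dose. It does not cover a known start on the dosing date with no time. It mentions a date/time for the end of an AE but only a date for onset, and Protocol 12.1.1 also speaks of an onset date. So the documents suggest, without confirming, that some AE times are recorded.

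**The case against.** The strongest reply is that little depends on these two variables. TEAE status, not onset day, is meant to separate pre-dose from post-dose events, and the AE tables are limited to TEAEs. No table named in SAP 7.8.2 uses onset day or duration. Single-dose saturation was measured from 0.5 to 24 hours, and SAP 7.8.5 and 7.9.1 summarise saturation and Ramsay scores by assessment time. Relatedness is the investigator's judgement and is not computed from onset day. SAP 6.1 lists all eCRF data, dose times are listed, and morphine times were recorded. With five subjects enrolled in Group B and none in C or D, reading individual cases is feasible.

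Most of this stands, and it confines the onset and duration point to listings and case interpretation. It does not remove it. Timepoint summaries miss events between assessments, SAP 7.9.1 reports apnoea only as yes/no frequencies, and the TEAE boundary has the gap shown in step 6.

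The 14-day window can be defended as matching the AE collection period and the 14-day element of the cut-off in Protocol 14.6.3. That justifies collecting and reporting late events. It does not justify reporting them only in a pooled count.

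A reader might infer that pre-dose, near-peak and next-morning events cannot be told apart at all. The documents do not support that. Next-morning events are normally Day 2, events on earlier dates get Day 0 or below, and any recorded AE time would appear in the listings.

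**Conclusion.** The point holds in two limited parts, and both should be acted on.

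- **Onset and duration.** Same-date events before dosing, near the assumed peak and later after dosing list as Day 1, and events of minutes and of many hours can both list as 1 day. The Day 1 result follows from the formula alone; only the percentages rest on the assumed peak and dosing hours. The effect is on listings and case interpretation. It would be wrong to conclude that a named safety table is distorted by these variables, or that pre-dose anaesthetic events are planned to be counted as TEAEs.
- **Pooling.** This part does affect planned tables. TEAE counts combine the period to EOT with a longer one in which other analgesics are allowed and post-operative pain is newly recorded. The 14-fold ratio applies to the single-dose phase only; in the multiple-dose phase, with the last dose at 18 hours, it is about 8.4. The documents give no event counts, so the number of TEAEs arising after EOT is unknown.

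Whether AE start times are on the eCRF, and whether the table shells in SAP Module 2 already split by period, cannot be seen from these documents.

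**What to change.** 1. In SAP 7.8.2, tabulate TEAEs separately for first dose to EOT and after EOT, using the cut at 24 hours after the last dose that SAP 4.4 already applies to medications.
2. In Table 8, state whether AE start and stop times are collected. Where they are, derive onset in hours from the most recent study-drug dose, and duration in minutes or hours for respiratory and sedation events. For morphine, give the time since the last bolus and show any background infusion, because time since last dose has no clear meaning during an infusion.
3. In SAP 6.3.1.1, count an AE that starts on the dosing date with no recorded time as a TEAE, in line with the worst-case principle used there. The existing rule for unknown onset suggests one exception: a recorded end before the first dose.

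While Table 8 is open, align its day counts. Study Day has no + 1, so the dosing date is Study Day 0 but AE Onset Day 1.

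The cost is a little more programming, smaller counts in each period, and missing hour-level values for AEs with no recorded time.

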6.3. Handling of Missing Data

Missing baseline assessments will not be imputed. For categorical variables with missing values, a category documenting the frequency of missing values will be displayed in the summary tables.

There will be no imputation of missing safety data, however missing relationship between AE and study medication will be considered as related to study medication following worst case principle. For AEs with missing severity, the most severe assessment will be imputed for analyses.

6.3.1. Imputation of Partial Dates

6.3.1.1. TEAE Status for Completely Unknown Start Date

The following rules will apply in cases where start date of an AE is completely unknown:

- If the AE onset date is unknown and the end date/time is on or after first dose or ongoing, then the AE will be considered a TEAE.
- If the AE onset date is unknown and the end date/time is before first dose, then the AE will not be considered a TEAE.

- If both the start and end dates are unknown (or end date is ongoing), then the AE will be considered a TEAE, following the worst-case principle.

If the AE onset date is partly present and month/year is prior to the first dose, then the AE will not be considered a TEAE.

6.3.1.2. Concomitant Status of Medication for Completely Unknown Start Date

The following rules will apply in cases where start date of concomitant medication is completely unknown:

- If the medication onset date is unknown and the end date/time is after the screening date but on or before 24 hours post first dose or the medication is ongoing, then the medication will be considered as concomitant.
- If the medication onset date is unknown and the end date/time is before the screening date, then the medication will not be considered as concomitant.
- If both the start and end dates are unknown, then the medication will be considered as concomitant. This approach is the most conservative following the worst-case principle.

If the medication onset date is partly present and month/year is prior to the first dose, then the medication will be considered as concomitant.

6.4. Treatment Groups

The data for the single-dose phase and the multiple-dose phase will be summarized separately.

The data for the single-dose phase will be summarized by age group and dose group. The multiple-dose phase will be summarized by age group and treatment group.

7. STATISTICAL ANALYSES

7.1. Subject Disposition

The subject disposition will be summarized separately for the single-dose phase and the multiple-dose phase.

The number and percentage of subjects screened, enrolled, completed, and withdrawn from the study, as well as reason of withdrawal from the study will be summarized.

A subject listing of disposition data will be provided. Reasons for screen failure will be listed. In addition, a subject listing by inclusion/exclusion criteria not met will be presented.

7.2. Protocol Deviations

The major and minor protocol deviation categories will be summarized separately for the single-dose phase and the multiple-dose phase. In addition, an overall summary of the protocol deviations for single-dose phase and multiple dose phase will be provided.

A listing of all protocol deviations will be presented.

7.3. Demographics and Baseline Characteristics

Demographics and baseline characteristics will be summarized separately by the single-dose phase and by the multiple-dose phase.

Age (days), height (cm), body weight (kg), and BMI (kg/m²) will be summarized as continuous variables using appropriate descriptive statistics.

Gender, race, and ethnicity will be summarized as categorical variables using frequency and percentages.

All demographic and baseline characteristics will be presented in a subject listing.

7.4. Medical and Surgical History

Medical and surgical history will be coded using MedDRA Version 19.0. Medical and surgical history by subject will be listed.

7.5. Prior, Concomitant and Follow-up Medications

Prior, concomitant, and follow-up medication use will be summarized separately by the single-dose phase and by the multiple-dose phase.

Prior, concomitant, and follow-up medications will be summarized using frequency and percentages by active ingredient within each ATC classification, with ATC classification and active ingredients ordered alphabetically. Multiple uses of the same medication by a subject will be counted only once.

A subject listing of medications indicating prior, concomitant, and follow-up classification will be presented. Additionally, the surgical procedures and surgical medications will be listed separately.

7.6. Efficacy Analysis

Only safety analyses are being conducted for this abbreviated CSR, hence no efficacy analyses will be conducted.

7.7. Rescue Medication

Rescue medication includes the total dose of morphine used and the duration of morphine (hours) use during the study, which will be summarized descriptively and will be presented separately for the single-dose and multiple-dose phases.

7.8. Safety Analyses

7.8.1. Study Drug Exposure

The total dose administered, total volume administered and duration of exposure (hours) will be summarized for subjects in the multiple-dose phase. The total volume administered during single-dose phase will also be summarized.

The study drug exposure details including the date/time of dose administration, route of administration, dose level and volume administered and whether food was consumed within 2 hours prior to or 1 hour after study drug administration will be presented in a subject listing.

7.8.2. Adverse Events

All AE summary tables will include only TEAEs, unless otherwise specified.

An overall summary of AE will be presented and will include the following:

- Total number of TEAEs reported
- Total number of TEAEs reported by severity
- Subjects with at least one treatment related TEAE
- Subjects with at least one severe TEAE
- Subjects with at least one Serious Adverse Events
- Subjects with at least one TEAE leading to drug interruption/withdrawals
- Subjects with at least one TEAE leading to deaths

TEAEs will be summarized by system organ class and PT. A subject will only be counted once per system organ class and PT.

For TEAEs summarized by severity (i.e., mild, moderate, severe), if a subject has multiple events occurring in the same system organ class or same PT, then the event with the maximum severity (i.e., severe) will be counted.

For the study drug related TEAEs, if a subject has multiple events occurring in the same system organ class or same PT, the event with the highest association (i.e., related) to study drug will be considered for analyses.

TEAEs will be presented in decreasing order of the incidence at system organ class level and within each system organ class, in decreasing order of the incidence at the PT level.

The following summary tables will be presented by system organ class and PT separately for the single-dose phase and the multiple-dose phase.

- All TEAEs.
- Serious TEAEs.
- TEAEs by severity.
- All study drug related TEAEs.
- TEAEs leading to study drug interruption/withdrawal.

The following listings will be presented by subject:

- All TEAEs.
- Serious TEAEs.
- AEs resulting in study drug withdrawal/interruption.
- AEs resulting in death.

